7.3.8 Hy's law

Cases where a patient shows elevations in liver biochemistry may require further evaluation and occurrences of AST or ALT $\geq 3 \times \text{ULN}$ together with total bilirubin $\geq 2 \times \text{ULN}$ may need to be reported as SAEs. Please refer to Appendix A for further instruction on cases of increases in liver biochemistry and evaluation of Hy's Law

7.3.9 Disease progression

Disease progression can be considered as a worsening of a patient's condition attributable to the disease for which the investigational product is being studied. It may be an increase in the severity of the disease under study and/or increases in the symptoms of the disease. The development of new, or progression of existing metastasis to the primary cancer under study should be considered as disease progression and not an AE. Events, which are unequivocally due to disease progression, should not be reported as an AE during the study.

Clinical Study Protocol - 6
Olaparib - ESR-18-13807

7.3.10 New Cancers

The development of a new primary cancer should be reported as an AE (see Section 8.3.13 Olaparib Adverse Events of Special Interest) and would in most cases meet seriousness criteria (with the exception of some non-melanoma skin cancers). New primary malignancies are those that are not the primary reason for the administration of the study treatment and have developed after the inclusion of the patient into the study. They do not include metastases of the original cancer. Symptoms of metastasis or the metastasis itself should not be reported as an AE/SAE, as they are considered to be disease progression.

7.3.11 Lack of efficacy

When there is deterioration in the cancer, for which the study treatment(s) is being used, there may be uncertainty as to whether this is lack of efficacy or an AE. In such cases, unless the Sponsor or the reporting physician considers that the study treatment contributed to the deterioration of the condition, or local regulations state to the contrary, the deterioration should be considered to be a lack of efficacy and not an AE.

7.3.12 Deaths

All deaths that occur during the study, or within the protocol-defined 30-day post-study follow-up period after the administration of the last dose of study treatment, must be reported as follows:

- Death clearly the result of disease progression should be reported to the study monitor at the next monitoring visit and should be documented in the CRF but should not be reported as an SAE.
- Where death is not due (or not clearly due) to progression of the disease under study, the AE causing the death must be reported to the study monitor as a SAE within **24 hours** (see Section 8.4.1 for further details). The report should contain a comment regarding the co-involvement of progression of disease, if appropriate, and should assign main and contributory causes of death. This information can be captured in the CRF.

Deaths with an unknown cause should always be reported as a SAE. A post mortem may be helpful in the assessment of the cause of death, and if performed a copy of the post-mortem results should be forwarded to AstraZeneca within the usual timeframes.

7.3.13 Olaparib adverse events of special interest

Adverse events of special interest [AESI] are events of scientific and medical interest specific to the further understanding of olaparib's safety profile and require close monitoring and rapid communication by the investigators to AstraZeneca. Adverse Events of Special Interest for olaparib are the Important Potential Risks of MDS/AML, new primary malignancy (other than MDS/AML) and pneumonitis.

A questionnaire will be sent to any investigator reporting an AESI, as an aid to provide further detailed information on the event. During the study there may be other events identified as

Clinical Study Protocol - 6
Olaparib - ESR-18-13807

AESIs that require the use of a questionnaire to help characterise the event and gain a better understanding regarding the relationship between the event and study treatment.

7.4 Safety reporting and medical management

7.4.1 Reporting of serious adverse events

All SAEs have to be reported, whether or not considered causally related to the investigational product, or to the study procedure(s). All SAEs will be recorded in the CRF.

If any SAE occurs in the course of the study, then Investigators or other site personnel inform the appropriate AstraZeneca representatives within one day i.e., immediately but **no later than 24 hours** of when he or she becomes aware of it.

The designated AstraZeneca representative works with the Investigator to ensure that all the necessary information is provided to the AstraZeneca Patient Safety data entry site **within 1 calendar day** of initial receipt for fatal and life threatening events **and within 5 calendar days** of initial receipt for all other SAEs.

For fatal or life-threatening adverse events where important or relevant information is missing, active follow-up is undertaken immediately. Investigators or other site personnel inform AstraZeneca representatives of any follow-up information on a previously reported SAE within one calendar day i.e., immediately but **no later than 24 hours** of when he or she becomes aware of it.

7.4.2 Pregnancy

All pregnancies and outcomes of pregnancy should be reported to AstraZeneca except for:

- If the pregnancy is discovered before the study patient has received any study drug

If a pregnancy is reported, the investigator should inform the sponsor within 24 hours of learning of the pregnancy.

Abnormal pregnancy outcomes (e.g., spontaneous abortion, fetal death, stillbirth, congenital anomalies, and ectopic pregnancy) are considered SAEs.

7.4.2.1 Maternal exposure

If a patient becomes pregnant during the course of the study, olaparib should be discontinued immediately.

Pregnancy itself is not regarded as an adverse event unless there is a suspicion that the investigational product under study may have interfered with the effectiveness of a contraceptive medication. Congenital abnormalities/birth defects and spontaneous miscarriages should be reported and handled as SAEs. Elective abortions without complications should not be handled as AEs. The outcome of all pregnancies (spontaneous miscarriage, elective termination, ectopic pregnancy, normal birth or congenital abnormality) occurring from the date of the first dose of

Clinical Study Protocol - 6
Olaparib - ESR-18-13807

study medication until 1 month after the last dose of study medication should be followed up and documented even if the patient was discontinued from the study.

If any pregnancy occurs in the course of the study, then the Investigator or other site personnel informs the appropriate AstraZeneca representatives within 1 day i.e., immediately but **no later than 24 hours** of when he or she becomes aware of it.

The designated AstraZeneca representative works with the Investigator to ensure that all relevant information is provided to the AstraZeneca Patient Safety data entry site within 1 or 5 calendar days for SAEs and within 30 days for all other pregnancies.

The same timelines apply when outcome information is available.

7.4.3 Overdose

There is currently no specific treatment in the event of overdose with olaparib and possible symptoms of overdose are not established.

Olaparib must only be used in accordance with the dosing recommendations in this protocol. Any dose or frequency of dosing that exceeds the dosing regimen specified in this protocol should be reported as an overdose. The Maximum Tolerated Dose is 300 mg twice daily (tablet).

Adverse reactions associated with overdose should be treated symptomatically and should be managed appropriately.

- An overdose with associated AEs is recorded as the AE diagnosis/symptoms on the relevant AE modules in the CRF.

If an overdose on an AstraZeneca study drug occurs in the course of the study, then the Investigator or other site personnel inform appropriate AstraZeneca representatives immediately, or **no later than 24 hours** of when he or she becomes aware of it.

The designated AstraZeneca representative works with the Investigator to ensure that all relevant information is provided to the AstraZeneca Patient Safety data entry site.

For overdoses associated with a SAE, the standard reporting timelines apply, see Section 7.3.2. For other overdoses, reporting must occur within 30 days.

7.4.4 Management of adverse events Dose Reductions

Any toxicity observed during the course of the study could be managed by interruption of the dose of study treatment or dose reductions. Repeat dose interruptions are allowed as required, for a maximum of 4 weeks on each occasion. If the interruption is any longer, the study team must be informed. Study treatment can be dose reduced to 250 mg twice daily as a first step and to 200

Clinical Study Protocol - 6
Olaparib - ESR-18-13807

mg twice daily as a second step. If the reduced dose of 200 mg twice daily is not tolerable, no further dose reduction is allowed, and study treatment should be discontinued.

Once dose is reduced, escalation is not permitted (except following concomitant treatment with CYP3A4 inhibitors – see Section 6.5

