3.3 Justification for dose

The dose of olaparib used in this study is 300 mg twice daily which is the currently FDA approved dose. Starting dose modifications based on the patient's medical condition, for example creatinine clearance, are allowed.

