5.6 Dose modification

Dose Reductions

Clinical Study Protocol - 6
 Olaparib - ESR-18-13807

In case a dose reduction is necessary, the Study treatment will be administered as follows:

Table 4 Dose reductions for olaparib to manage adverse events

Initial Dose	Following re-challenge post interruption: Dose reduction 1	Dose reduction 2
300 mg twice daily	250 mg twice daily	200 mg twice daily
250 mg twice daily	200 mg twice daily	150 mg twice daily
200 mg twice daily	150 mg twice daily	100 mg twice daily

Table 5 Dose reduction for olaparib if patient develops moderate renal impairment

Initial Dose	Moderate renal impairment (calculated creatinine clearance by Cockcroft -Gault equation or based on a 24 hour urine test between 31 and 50 ml/min): Dose reduction
300 mg twice daily	200 mg twice daily

If starting dose is 200 mg twice daily, and patient develops renal impairment, dose modification will be determined by the treating physician.

Table 6 Dose reductions for olaparib if patient has to start taking a strong or moderate CYP3A inhibitor

Initial Dose	Strong CYP3A inhibitor	Moderate CYP3A inhibitor
300 mg twice daily	100 mg twice daily	150 mg twice daily

If starting dose is 200 mg twice daily, and patient is required to take a strong or moderate CYP3A inhibitor, dose modification will be determined by the treating physician.

For guidance on dose reductions for management of AEs (including renal impairment) refer to Section 8.4.4.

For guidance on dose reductions when concomitant strong or moderate CYP3A inhibitors cannot be avoided see Section 6.5.

When dose reduction is necessary patients will take one 150 mg tablet and one 100 mg tablet twice daily or two x 100 mg tablet twice daily (see Section 8.4.4), or one 150 mg tablet twice daily or one 100 mg tablet twice daily (see Section 6.5).

Folic Acid dose modification:

Clinical Study Protocol - 6
Olaparib - ESR-18-13807

Patients with folate deficiency will start folic acid supplementation at 1 mg daily. If they continue to have a Hgb less than 10 g/dl (grade 2) and folate deficiency despite folate supplementation, folic acid dose can be increased to 2 mg daily or higher at the discretion of the investigator.

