7.4.4.8 Interruptions for intercurrent non-toxicity related events

Study treatment dose interruption for conditions other than toxicity resolution should be kept as short as possible. If a patient cannot restart study treatment within 4 weeks for resolution of intercurrent conditions not related to disease progression or toxicity, the case should be discussed with AZ study physician.

All dose reductions and interruptions (including any missed doses), and the reasons for the reductions/interruptions are to be recorded in the eCRF.

Study treatment should be stopped at least 3 days prior to planned surgery. After surgery study treatment can be restarted when the wound has healed. No stoppage of study treatment is required for any needle biopsy procedure.

Study treatment should be discontinued for a minimum of 3 days before a patient undergoes radiation treatment. Study treatment should be restarted within 4 weeks as long as any bone marrow toxicity has recovered.

Because the AEs related to olaparib may include asthenia, fatigue and dizziness, patients should be advised to use caution while driving or using machinery if these symptoms occur.

Table 10 Dose reductions for study treatment

Initial Dose	Following re-challenge post interruption: Dose reduction 1	Dose reduction 2
300 mg twice daily	250 mg twice daily	200 mg twice daily
250 mg twice daily	200 mg twice daily	150 mg twice daily
200 mg twice daily	150 mg twice daily	100 mg twice daily

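### For patients who start olaparib below 300 mg twice daily, the stopping rule in Section 7.4.4 contradicts the reduction steps listed in Tables 4 and 10

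*Combined protocol and SAP*

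**What the plan says.** Section 7.4.4 of the combined protocol and SAP deals with any toxicity. It gives 250 mg twice daily as the first reduction and 200 mg twice daily as the second, then states: "If the reduced dose of 200 mg twice daily is not tolerable, no further dose reduction is allowed, and study treatment should be discontinued". Nothing there limits the sentence to a particular starting dose.

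Table 4 in Section 5.6 covers the same situation; its title reads "Dose reductions for olaparib to manage adverse events". It is arranged by initial dose. The rows (initial dose, first reduction, second reduction) are:

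- "300 mg twice daily 250 mg twice daily 200 mg twice daily"
- "250 mg twice daily 200 mg twice daily 150 mg twice daily"
- a 200 mg start, with steps to 150 and 100 mg.

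"Table 10 Dose reductions for study treatment" repeats these rows inside Section 7.4.4.8, including "200 mg twice daily 150 mg twice daily 100 mg twice daily".

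Patients who start below 300 mg are foreseen. Section 3.3 says: "Starting dose modifications based on the patient's medical condition, for example creatinine clearance, are allowed". Section 5.6 names one such start: "If starting dose is 200 mg twice daily, and patient develops renal impairment, dose modification will be determined by the treating physician". Inclusion criterion 11 also admits patients with out-of-range laboratory values, provided the package insert is followed for dose adjustment.

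Section 2 lists dose reduction and drug discontinuation as separate parts of a secondary endpoint, and Section 8.4.1 compares them among randomized patients.

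**The concern.** Two instructions in force for the same adverse events give different answers on whether a patient may continue olaparib. One of the two tables sits within Section 7.4.4 itself, so a site reading only that section meets both.

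The first thing at stake is patient safety, because the conflict concerns when the drug must be stopped. The second is the data. The study is multi-center, and two sites could manage the same clinical course differently while each follows a passage of the protocol. One patient would then be recorded as having discontinued olaparib and the other would not. Discontinuation is one of the outcomes on which folic acid supplementation is to be judged.

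**Working it through.** The plan states no figure to reproduce here. The check sets each table row against the floor in Section 7.4.4.

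| Starting dose (twice daily) | Steps in Tables 4 and 10 | Steps below 200 mg | Compared with Section 7.4.4 |
|---|---|---|---|
| 300 mg | 250, then 200 mg | 0 | Agrees |
| 250 mg | 200, then 150 mg | 1 | Conflicts at the second step |
| 200 mg | 150, then 100 mg | 2 | Unclear whether the floor applies |

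Three rows with two steps each give 3 × 2 = 6 listed steps. Of these, 0 + 1 + 2 = 3 are below 200 mg, and they fall in two of the three rows.

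**250 mg start.** After one reduction the patient is at 200 mg, which is a reduced dose in the plainest sense. If it is not tolerated, Section 7.4.4 requires discontinuation, while Tables 4 and 10 list 150 mg. Both cannot be followed.

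**200 mg start.** Here 200 mg is the starting dose. Section 7.4.4 speaks of a reduced dose of 200 mg, so it may or may not be meant to cover this patient. The text does not say.

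Other passages were then checked to see whether they settle the matter. They do not.

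- The tablet instruction at the end of the olaparib part of Section 5.6 points to the adverse-event section for the 250 and 200 mg combinations, and only to the CYP3A section for 150 and 100 mg. (It cites Sections 8.4.4 and 6.5; in the current numbering that content is in 7.4.4 and 5.5.) This sits badly with Table 4 in the same section, which lists 150 and 100 mg for adverse events.
- Section 7.4.4.5 repeats the 250-then-200 mg steps and then sends the reader to Section 5.6 for more guidance, so it invokes both rules.
- Table 8 (anaemia) and Table 9 (neutropenia, leukopenia and thrombocytopenia) also give only 250 mg and then 200 mg. For a 250 mg start the first of these is no reduction, and for a 200 mg start it is above the current dose.

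**The case against.** The best defence is that Section 7.4.4 was written for the standard start. A first step to 250 mg and a second to 200 mg is possible only from 300 mg, and the floor follows directly on that sequence. Table 4 is arranged by initial dose, and Section 7.4.4.5 refers readers to it. On this reading the text covers 300 mg starters, the tables cover everyone else, and nothing conflicts.

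That may well be the intention, but it is not written. The floor carries no restriction by starting dose, and the tablet instruction points the other way by tying 150 and 100 mg to CYP3A inhibitors alone. The objection does limit the scope of the point. A reader might infer that the dose rules contradict each other for every patient; the documents do not support that, because text and tables match for a 300 mg start. The 200 mg start is also the weaker of the two remaining cases, yet it is the only lower start named in running text. A 250 mg start appears only as a table row, so the clear conflict may concern few patients.

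The other objections concern impact. Allocation is 1:1, so the ambiguity is not attached to one arm. The endpoint is secondary in a pilot study. Reductions, interruptions and discontinuations are entered in the eCRF as they happen. All of this stands: it means that no direction of bias follows from the wording alone and that the endpoints need no new definition. It does not remove the problem that what happens to the patient can depend on which passage is read.

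**Conclusion.** The plan is wrong as written for olaparib starts below 300 mg twice daily. The contradiction is outright for a 250 mg start reduced to 200 mg, and the rule is unclear for a 200 mg start. It rests on the wording of the passages and on no numerical assumption beyond the protocol's own permission for lower starts.

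Two stronger conclusions are tempting and should not be drawn. First, a reader might infer that one clinical course counts as a dose reduction under one rule and as a discontinuation under the other. In the clear case this fails: the 250 mg starter at 200 mg has already had a dose reduction under both, so only discontinuation status can differ. Second, a reader might try to size the effect from the 26% dose-reduction and 6% discontinuation rates that the Background quotes from an earlier ovarian maintenance trial. The documents give no share of patients starting below 300 mg. The 26% is not given as a rate of failing an already reduced dose, which is what a 250 mg starter must do to reach the conflict. The comparison in Section 8.4.1 is among randomized patients, not all 75. The number affected therefore cannot be estimated.

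The primary endpoint, folate below 7 ng/mL within three months, is not defined by dose changes and is not affected.

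**What to change.** Reconcile Section 5.6 (Table 4 and the tablet instruction), the floor in Section 7.4.4 and Table 10 in Section 7.4.4.8, so that one consistent rule is stated for each permitted starting dose. Check the 250-then-200 mg steps in Tables 8 and 9 and Section 7.4.4.5 against that rule and state which starting doses they cover. The content of the rule is for the medical team. Stating it once and cross-referring to it elsewhere would keep the passages from diverging again.

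The cost is amendment wording. The endpoint definitions, sample size and planned analyses need no change on this account.

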7.4.4.1 Management of haematological toxicity

7.4.4.2 Management of anaemia

Table 8 Management of anaemia

Haemoglobin	Action to be taken
Hgb < 10 but ≥ 8 g/dl (CTCAE Grade 2)	
First occurrence: Give appropriate supportive treatment and investigate causality. Investigator judgement to continue olaparib with supportive treatment (e.g., transfusion) or interrupt dose for a maximum of 4 weeks. Study treatment can be restarted if Hb has recovered to > 9g/dl.
 
Subsequent occurrences: If Hgb < 10 but ≥ 9 g/dl investigator judgement to continue olaparib with supportive treatment (e.g., transfusion) or dose interrupt (for max of 4 weeks) and upon recovery dose reduction may be considered (to 250 mg twice daily as a first step and to 200 mg twice daily as a second step). If Hgb < 9 but ≥ 8 g/dl, dose interrupt (for max of 4 weeks) until Hb ≥ 9 g/dl and upon recovery dose reduction may be considered (to 250 mg twice daily as a first step and to 200 mg twice daily as a second step).

Hgb < 8 g/dl (CTCAE Grade 3)	
Give appropriate supportive treatment (e.g., transfusion) and investigate causality. Interrupt olaparib for a maximum of 4 weeks until improved to Hgb ≥ 9 g/dl. Upon recovery dose reduce to 250 mg twice daily as a first step and to 200 mg twice daily as a second step in the case of repeat Hgb decrease.

Common treatable causes of anemia (e.g., iron, vitamin B12 or folate deficiencies and hypothyroidism) should be investigated and appropriately managed. In some cases management of anemia may require blood transfusions. For cases where patients develop prolonged haematological toxicity (≥2 week interruption/delay in study treatment due to CTC grade 3 (Hgb less than 8.0 g/dl) or worse anemia and/or development of blood transfusion dependence), refer to guidance later in this section for the management of this.

Clinical Study Protocol - 6
Olaparib - ESR-18-13807

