
Moderate CYP3A inhibitors:
 
ciprofloxacin, erythromycin, diltiazem, fluconazole, verapamil
	
 • Strong CYP3A inhibitors – reduce the dose of olaparib to 100 mg twice daily for the duration of concomitant therapy with the strong inhibitor and for 5 half-lives afterwards. • Moderate CYP3A inhibitors - reduce the dose of olaparib to 150 mg twice daily for the duration of concomitant therapy with the moderate inhibitor and for 3 half-lives afterwards. • After the washout of the inhibitor is complete, the olaparib dose can be re-escalated.

Table 3 Restricted concomitant medications

Medication/class of drug:	Usage (including limits for duration permitted and special situations in which it's allowed):

Strong inducers:
 
phenobarbital, phenytoin, rifampicin, rifabutin, rifapentine, carbamazepine, nevirapine, enzalutamide and St John's Wort
	
Strong or moderate CYP3A inducers should not be taken with olaparib.
 
If the use of any strong or moderate CYP3A inducers are considered necessary for the patient's safety and welfare this could diminish the clinical efficacy of olaparib.

Moderate CYP3A inducers:
 
bosentan, efavirenz and modafinil
	
If a patient requires use of a strong or moderate CYP3A inducer then they must be monitored carefully for any change in efficacy of olaparib.

 • CYP3A4 substrates: hormonal contraceptive, simvastatin, cisapride, cyclosporine, ergot alkaloids, fentanyl, pimozide, sirolimus, tacrolimus and quetiapine • CYP2B6 substrates: bupropion, efavirenz • OATP1B1 substrates: bosentan, glibenclamide, repaglinide, statins and valsartan • OCT1, MATE1 and MATE2K substrates: metformin • OCT2 substrates: serum creatinine • OAT3 substrates: furosemide, methotrexate 	
Effect of olaparib on other drugs
 
Based on limited in vitro data, olaparib may increase the exposure to substrates of CYP3A4, OATP1B1, OCT1, OCT2, OAT3, MATE1 and MATE2K.
 
Based on limited in vitro data, olaparib may reduce the exposure to substrates of 2B6.
 
Caution should be observed if substrates of these isoenzymes or transporter proteins are co-administered.

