7.4.4.3 Management of neutropenia, leukopenia and thrombocytopenia

Table 9 Management of neutropenia, leukopenia and thrombocytopenia

Toxicity	Study treatment dose adjustment
CTCAE Grade 1-2	Investigator judgement to continue treatment or if dose interruption, this should be for a maximum of 4 weeks; appropriate supportive treatment and causality investigation
CTCAE Grade 3-4	Dose interruption until recovered to CTCAE gr 1 or better for a maximum of 4 weeks. If repeat CTCAE grade 3-4 occurrence, dose reduce olaparib to 250 mg twice daily as a first step and 200 mg twice daily as a second step

Adverse event of neutropenia and leukopenia should be managed as deemed appropriate by the investigator with close follow up and interruption of study drug if CTC grade 3 or worse neutropenia occurs.

Primary prophylaxis with Granulocyte colony-stimulating factor (G-CSF) is not recommended, however, if a patient develops febrile neutropenia, study treatment should be stopped and appropriate management including G-CSF should be given according to local hospital guidelines. Please note that G-CSF should not be used within at least 24 h (7 days for pegylated G-CSF) of the last dose of study treatment unless absolutely necessary.

Platelet transfusions, if indicated, should be done according to local hospital guidelines.

For cases where patients develop prolonged haematological toxicity (≥ 2 week interruption/delay in study treatment due to CTC grade 3 or worse), refer to guidance later in this section for the management of this.

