7.4.4.9 Renal impairment

If subsequent to study entry and while still on study therapy, a patient's estimated CrCl falls below the threshold for study inclusion (≥ 51 ml/min), retesting should be performed promptly.

A dose reduction is recommended for patients who develop moderate renal impairment (calculated creatinine clearance by Cockcroft-Gault equation or based on a 24 hour urine test of between 31 and 50 ml/min) for any reason during the course of the study: the dose of olaparib *or* should be reduced to 200 mg twice daily.

Because the CrCl determination is only an estimate of renal function, in instances where the CrCl falls to between 31 and 50 mL/min, the investigator should use his or her discretion in determining whether a dose change or discontinuation of therapy is warranted.

Clinical Study Protocol - 6
Olaparib - ESR-18-13807

Olaparib has not been studied in patients with severe renal impairment (creatinine clearance ≤ 30 ml/min) or end-stage renal disease; if patients develop severe impairment or end stage disease is it recommended that olaparib be discontinued.

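### The olaparib dose-reduction rules contradict each other for patients already at or below 200 mg twice daily

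*Combined protocol and SAP*

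**What the plan says.** Two sets of rules set the olaparib dose, and they are written independently.

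**Toxicity steps.** These are fixed amounts.
- Table 8 (7.4.4.2), for haemoglobin below 8 g/dl: "Upon recovery dose reduce to 250 mg twice daily as a first step and to 200 mg twice daily as a second step".
- Table 9 (7.4.4.3), for repeat grade 3-4 neutropenia, leukopenia or thrombocytopenia: "dose reduce olaparib to 250 mg twice daily as a first step and 200 mg twice daily as a second step".
- The lead-in to 7.4.4 and section 7.4.4.5 offer the same two steps as an option, as does the grade 2 row of Table 8 for subsequent occurrences.
- 7.4.4 adds a floor: if 200 mg is not tolerated, there is no further reduction and treatment stops.
- 7.4.4 also adds a bar on increases: "Once dose is reduced, escalation is not permitted (except following concomitant treatment with CYP3A4 inhibitors".

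**Reductions for other reasons.**
- Moderate renal impairment (Table 5 and 7.4.4.9): the dose "should be reduced to 200 mg twice daily".
- Strong CYP3A inhibitor (Table 3, repeated in Table 6): "reduce the dose of olaparib to 100 mg twice daily for the duration of concomitant therapy with the strong inhibitor".
- Moderate CYP3A inhibitor (same tables): "reduce the dose of olaparib to 150 mg twice daily for the duration of concomitant therapy with the moderate inhibitor".
- Table 3 allows the dose to go back up only after the inhibitor has washed out.

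**Step tables.** Tables 4 (5.6) and 10 (7.4.4.8) are identical. They give two steps by *Initial Dose*: 300 to 250 to 200, 250 to 200 to 150, and 200 to 150 to 100 mg twice daily.

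**The concern.** The fixed toxicity steps suit a patient on 300 mg twice daily. They do not say what happens when the dose is already at or below a named step for another reason. Such patients are foreseeable. Section 3.3 allows a lower starting dose, for example for creatinine clearance. Inclusion item 11 admits patients with laboratory values outside the entry range. Tables 3, 5 and 6 exist for patients who need a lower dose on study.

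Anaemia is the toxicity this trial is built around, so the step after grade 3 anaemia should be clear at the bedside. As written, two sites could handle the same patient differently and each could cite the protocol. Section 7.4.3 also makes any dose above the specified regimen reportable as an overdose. A site following Table 8 against Table 3 could therefore have to report having done so.

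**Working it through.** There is no sample size or power figure to reproduce. The check compares each named step with each reduced dose the protocol allows, then reads the remaining rules against the result. All doses are twice daily.

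**Step 1. Arithmetic.** Inputs are the steps of 250 and 200 mg (Tables 8 and 9, 7.4.4, 7.4.4.5) and the reduced doses of 200 mg (Table 5, 7.4.4.9), 150 mg and 100 mg (Tables 3 and 6). Change = step / current dose − 1.

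| Current dose and reason | First step, 250 mg | Second step, 200 mg |
|---|---|---|
| 200 mg, renal impairment | 250/200 − 1 = +25% | 200/200 − 1 = 0% |
| 150 mg, moderate inhibitor | 250/150 − 1 = +67% | 200/150 − 1 = +33% |
| 100 mg, strong inhibitor | 250/100 − 1 = +150% | 200/100 − 1 = +100% |

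In no cell is the named step a reduction.

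**Step 2. A patient who started at 300 mg, is on 200 mg for renal impairment, and recovers from haemoglobin below 8 g/dl.**
- Table 8: 250 mg.
- Tables 4 and 10, if *Initial Dose* means the dose at study start (300 mg row): 250 mg.
- Tables 4 and 10, if it means the dose before the interruption (200 mg row): 150 mg.
- 7.4.4: no escalation, so not 250 mg; no reduction below 200 mg, so not 150 mg; discontinuation if 200 mg is not tolerated.

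These cannot all be followed.

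**Step 3. A patient on 150 or 100 mg because of a CYP3A inhibitor.**
- Table 8: 250 mg.
- Table 3: stay at 150 or 100 mg while the inhibitor continues, and for 3 or 5 half-lives afterwards.
- 7.4.4: an increase is allowed only following inhibitor treatment. The patient is also already below the 200 mg floor.
- Tables 4 and 10: no row for 150 or 100 mg. Read by dose at study start, the 300 mg row gives 250 mg.

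No toxicity step from 150 or 100 mg is written anywhere.

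**Step 4. The 200 mg floor against the step tables.** This conflict needs no on-study renal or CYP3A event. For an initial dose of 200 mg, Tables 4 and 10 go to 150 and then 100 mg. For 250 mg they end at 150 mg. Section 7.4.4 allows nothing below 200 mg. The tablet instructions at the end of the olaparib part of 5.6 link 250 and 200 mg to adverse-event management and 150 and 100 mg to CYP3A inhibitors, which again differs from the lower rows of Table 4 in the same section.

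**Step 5. Does a discretion clause cover the gap?** The two treating-physician clauses in 5.6 apply to a 200 mg starting dose followed by a renal or CYP3A event, not to a dose reduction followed by toxicity. The investigator discretion in 7.4.4.9 concerns the response to the fall in creatinine clearance, not a later cytopenia.

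**Step 6. Can the reader find the governing rule?** Section 7.4.4 refers to Section 6.5 for the CYP3A exception, and 5.6 refers to 6.5 and 8.4.4. None of these exists in the current numbering. The content is in 5.5 and 7.4.4.

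**The case against.** The strongest reply is that no careful reader would raise the dose. Table 8 speaks of reducing, an increase is not a reduction, and the lead-in to 7.4.4 bars escalation. The only exception follows inhibitor treatment, and Table 3 ties it to completed washout. This stands. A reader might infer from Table 8 alone that the protocol orders a higher dose after grade 3 anaemia, but the documents taken together do not support that. What the bar on escalation does not do is say what the step then is.

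A second reply is that *Initial Dose* in Tables 4 and 10 can mean the dose before the interruption, because the next column concerns re-challenge. A patient on 200 mg then has downward steps, and 7.4.4.5 does send readers to 5.6. That reading is open, but so is the other. Tables 5 and 6 in 5.6 use the same heading and are followed by sentences about the starting dose. Even on the pre-interruption reading, 150 and 100 mg have no row and the 200 mg floor is breached. One could limit the floor to patients who start at 300 mg, but 7.4.4 does not say so.

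A third reply is that the scope is narrow, and this also stands. Only the grade 3 row of Table 8 and the grade 3-4 row of Table 9 are directive. Strong and moderate CYP3A inhibitors are excluded at entry and discouraged on study. Entry normally requires creatinine clearance of at least 51 mL/min. The patient must have both a prior reduction and a serious cytopenia, in a study of 75.

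Finally, a reader might infer that the secondary outcome of dose reduction would be mis-scored, with an increase counted as a first-step reduction. The documents do not support this. Nothing scores reductions by step label. Sections 5.4 and 7.4.4.8 require dose changes to be recorded, with reasons required in 7.4.4.8 and, for CYP3A reductions, in Table 3.

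**Conclusion.** The point holds as an internal contradiction. For a patient at or below 200 mg twice daily, the fixed toxicity steps, the renal and CYP3A rules, the bar on escalation, the 200 mg floor and the step tables cannot all be followed. The named first step lies 25%, 67% or 150% above the current dose of 200, 150 or 100 mg. These figures measure how far the passages disagree; they are not dose increases that the protocol orders.

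The arithmetic rests only on doses printed in the protocol. The 150 mg answer for the renal patient depends on reading *Initial Dose* as the dose before interruption. The conflict between the 200 mg floor and the lower rows of Tables 4 and 10 depends on taking the floor in 7.4.4 as general, as it is worded. The documents give no figure for how many patients would be affected, and the number may be small. The matter deserves correction because it concerns dosing after serious haematological toxicity and is cheap to settle. It does not affect the sample size, the primary endpoint or the analysis in 8.4.1.

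**What to change.** Reconcile 7.4.4, Table 8, Table 9 and 7.4.4.5 with Tables 3 to 6, Table 10 and 7.4.4.9. Specifically:

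- Define *Initial Dose* in Tables 4 and 10 as either the dose at study start or the dose before the interruption.
- State which passage governs when a patient's current dose is already at or below a named step, including patients on 150 or 100 mg because of a CYP3A inhibitor.
- Bring the 200 mg floor in 7.4.4 and the 150 and 100 mg steps in Tables 4 and 10 into agreement.
- Correct the references to Sections 6.5 and 8.4.4.

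The sponsor's clinicians decide the dose levels; none is proposed here. No change to 8.4.1 is needed. The cost is a protocol clarification, with no new data, visits or analyses.
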